4.1 Enrolled Subjects

Enrolled subjects consists of all subjects who have signed informed consent and some study procedures have begun (e.g., start of eDiary).

4.2 Randomized Set

The Randomized Set will consist of all subjects who have been randomized into a treatment sequence.

4.3 Safety Set

The Safety Set will consist of all subjects who have taken at least 1 dose of investigational product.

4.4 Full Analysis Set

The Full Analysis Set (FAS) will consist of all subjects in the Safety Set who have at least 1 post-baseline (e.g., randomization) primary efficacy assessment (e.g. a diary entry).

4.5 Pharmacokinetic Set

The Pharmacokinetic Set will consist of all subjects in the Safety Analysis Set with no major deviations related to investigational product intake and evaluable PK profiles. (Note: subjects with missing data in some, but not all the periods, will be included in the analysis set.)

4.6 Pharmacodynamic Set

The Pharmacodynamic Set will consist of all subjects in the Safety Analysis Set for whom the primary pharmacokinetic data is considered sufficient and interpretable.

5. SUBJECT DISPOSITION

The number of subjects who have been enrolled and randomized and included in each subject population set (i.e., Safety, Full Analysis Set, Pharmacokinetic and Pharmacodynamic) will be summarized by treatment sequence, by treatment and overall. The denominator for the percentage calculation will be the number of randomized subjects for the Safety Set, and the number of subjects in the Safety Set for the Full Analysis Set, Pharmacokinetic and Pharmacodynamic Set.

The number and percentage of subjects who completed and prematurely discontinued during the study will be presented for each treatment sequence, treatment at time of discontinuation and overall for the Safety Set. Primary reasons for premature discontinuation from the study as recorded on the termination page of the eCRF will be summarized (number and percentage) by treatment sequence and by most recent treatment received at time of discontinuation for the Safety Set.

Subject disposition, subjects completing and terminating the study, and study analysis sets will be listed by subject for all Enrolled Subjects.

6. PROTOCOL VIOLATIONS AND DEVIATIONS

A summary of the number and percentage of subjects in the Safety Set with protocol violations or deviations will be produced.

For those subjects who enter the observation period but discontinue prior to randomization or who discontinue after randomization but prior to receiving study drug, a listing of those subjects will be provided.

All protocol violation and deviation data will be listed for the Enrolled Subjects with a flag for inclusion in the Safety Set.

7. DEMOGRAPHIC AND OTHER BASELINE CHARACTERISTICS

Demographic and baseline characteristics will be determined using the screening visit (Day -1) or last observation prior to the dose of investigational product, whichever is later. Descriptive summaries of demographic and baseline characteristics will be presented by treatment sequence for the Safety Set.

Subject demographics including age, sex, race, ethnicity, weight, height, and BMI will be summarized by treatment sequence for the Safety Set. Continuous variables will be summarized by descriptive statistics including number of subjects, mean, standard deviation, median, minimum, and maximum. Categorical variables will be summarized by the number of subjects in each category and the percentage of subjects out of the total in the respective analysis set.

Height and weight will be used to calculate BMI using the formula below:

$$\text{BMI} = \frac{\text{weight [kg]}}{(\text{height [m]})^2}$$

A listing will be created to show all the demographics and baseline characteristics for all Enrolled Subjects.

7.1 Medical History

All medical history findings that have been present/active within 1 year prior to enrollment will be recorded in the eCRF regardless of clinical relevance or presence at study start. Medical history will be summarized by treatment sequence for the Safety Set and listed for all subjects in the Enrolled Subjects.

7.2 HAE History

The following information associated with HAE history will be recorded in the eCRF at the screening visit (NOTE: the attack rate may be estimated based on subject or parent/caregiver recall as well as the subject's medical records):

- HAE Type (I or II).
- Any first-degree blood relative (i.e., mother, father, sibling) diagnosed with HAE. (yes/no). If yes, provide the relationship of first-degree blood relative(s).
- Any therapy received during the 9 months prior to screening for management of HAE (yes/no) (see Protocol Section 6.3.1).
- Total number, typical locations, average overall duration (days), and average overall severity of HAE attacks experienced during the 3 months prior to screening (see Protocol Section 6.10.1 for definition of severity).
- Prior HAE On Demand Acute Treatment, Prior HAE Long-Term Prophylaxis, Prior HAE Pre-Procedure/Short-Term Prophylaxis

HAE history will be summarized by treatment sequence for the Safety Set and listed for all Enrolled Subjects.

8. EXTENT OF EXPOSURE AND TREATMENT COMPLIANCE

8.1 Exposure to Investigational Product

A listing will be created by subject and treatment period and will show the date and time of dose administration for each treatment given for the Safety Set.

8.2 Measurement of Treatment Compliance

Investigational product dosing compliance for a specified period is defined as the total number of doses (each dose of study drug will consist of a single IV injection, total volume of 10 mL) actually taken by a subject during that period divided by the number of doses expected to be taken during the same period multiplied by 100. The total number of doses actually taken is calculated by the sum of the number of doses administered on Study Drug Exposure Log. The number of doses expected to be taken for a specified period is calculated as the number of weeks in that period multiplied by the number of doses to be taken per week during that period.

9. PRIOR AND CONCOMITANT MEDICATION

The version dated 01 Mar 2014 of the WHO Drug Dictionary will be used to classify prior and concomitant medications by preferred drug name.

Any therapy received during the 9 months prior to screening for the management of angioedema attacks should be recorded, including overall start and stop dates if known, and the HAE indication (i.e., long-term prevention, acute treatment, short-term prevention). For any medication used in the management of HAE that has a start date prior to Treatment Period 1 and is planned to be continued in the treatment periods of the study, a stop date prior to the first dose of study drug in Treatment Period 1 should be entered into the eCRF. Any subsequent use of this medication should be recorded as a concomitant medication with a new start date.

HAE therapy received 9 months prior to screening will be recorded. Otherwise all medications taken within 1 week prior to Day 1 of Treatment Period 1 will be recorded and entered into the eCRF.

Concomitant treatment refers to all treatment taken between the dates of the first dose of investigational product and the end of the follow-up period, inclusive.

Concomitant medications taken from the start of dosing through 1-week post-treatment will be recorded in the eCRF. For medications associated with management of angioedema attacks, study personnel will record the start/stop dates, dose, unit, frequency, route of administration, and indication (if known) in the subject's eCRF. For medications not associated with the management of HAE, study personnel will record the start/stop dates, route of administration, and indication for which the medication was administered in the subject's eCRF.

Prior medication usage will be summarized by the number and percentage of subjects receiving each medication by treatment sequence within the Safety Set. Concomitant medication usage will be summarized by the number and percentage of subjects receiving each medication by treatment within the Safety Set. Medications can be counted both as prior and as concomitant medication. Multiple medication usage by a subject in the same preferred term category will be counted only once. Concomitant medications will also be summarized by the number and percentage of subjects receiving each medication by treatment within the Safety Set. For this summary, concomitant medications will be assigned to a treatment if they are recorded at least once within the period corresponding to that treatment.

All non-study medications taken during the study will be listed and prior, concomitant (taken from the start of dosing through 1-week post-treatment in the eCRF) and post medications (taken after the 2nd period) will be flagged.

10. EFFICACY ANALYSES

All efficacy analyses will be based on the Full Analysis Set (FAS). The listing of all efficacy variables will be provided for the small sample trial.

10.1 Primary Efficacy Variable(s) and Analysis

The primary efficacy variable is number of angioedema attacks, normalized to a 12-week treatment period.

Analysis of the primary efficacy variable will employ descriptive statistics and will include all subjects randomized and treated with study drug in FAS. Graphic presentation will be provided to view the angioedema attack pattern from the crossover designed study using FAS with both period completers. If warranted by the data, the comparison of CINRYZE doses will employ a paired t-test to perform a two-sided test of superiority (1000 U vs. 500 U) conducted at $\alpha=0.1$, this comparison will be performed only if the final sample size has 12 or more complete subjects with both period data. The test has low power and so we cannot assert that the lack of significance implies lack of effect.

If the final data 12 or more complete subjects, the between treatment comparison will be performed to test the null hypothesis:

$$H_0: \mu_{\Delta(1000-500)} = 0,$$

against the alternative hypothesis:

$$H_a: \mu_{\Delta(1000-500)} \neq 0$$

Where $\mu_{\Delta(1000-500)}$ is the population mean of within subject treatment difference for the primary efficacy variable assessed by the point estimate of the sample mean calculated as following:

$$\hat{\mu}_{\Delta(1000-500)} = \bar{x}_{\Delta(1000-500)} = \frac{\sum_{i=1}^N (x_{1000i} - x_{500i})}{N}$$

,and the corresponding 90% CI will be provided for the point estimate.

Treatment and treatment sequence effects will be tested using mixed effects model at $\alpha=0.1$, with period, treatment and treatment sequence as fixed effects, and subject nested within sequence as random effect. Adjusted means and 90% CIs will be calculated for both treatments, for both sequences and overall; as well as for the difference between the treatments.

To account for any potential carryover effect, sensitivity analysis using the paired t-test and mixed effect models will be performed by excluding any attacks occurring within the first 2 weeks of Treatment Period 2 for both sequences during which carryover effect is suspected to be maximal.

Furthermore, the sensitivity analysis by will be repeated by excluding first 2 weeks of both treatment periods for both sequences to account for the washout and potential carryover effect.

The following analyses will be performed to explore the potential weight-adjusted dose response relationship in efficacy. The adjusted dose is defined as period specific dose (500 U or 1000 U) divided by the period specific baseline weight (kg). Period specific baseline weight is the weight prior to the first dose in each treatment period. The adjusted dose will be spitted into 4 groups according to 25th, 50th and 75th percentiles of the adjusted dose. Descriptive statistics of the primary efficacy variable will be presented for each of the four dose groups based on the quartiles. The pairwise differences in mean response among the four groups (6 pairs: group 1 versus 2, 1 vs 3, 1 vs 4, 2 vs 3, 2 vs 4, 3 vs 4) will be estimated using the mixed effects model at $\alpha=0.1$, with period, dose group and treatment sequence as the fixed effects, and subject nested within sequence as random effect. In addition, the weight-adjusted dose response slope for the continuous weight-adjusted dose will be estimated by the mixed effect model at $\alpha=0.1$, with period, dose and treatment sequence as the fixed effects and subject nested within sequence as random effect.

The scatter plot of normalized number of angioedema attacks versus weight-adjusted dose will be provided.

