4.2 Exclusion Criteria

To be eligible for this protocol, a subject must not:

1. Have a history of hypercoagulability (abnormal blood clotting).
2. Have a diagnosis of acquired angioedema or known to have C1 INH antibodies.
3. Have a history of allergic reaction to C1 INH products, including CINRYZE (or any of the components of CINRYZE), or other blood products.
4. Be pregnant or breastfeeding.
5. Have received an investigational drug other than those required for prevention or treatment of angioedema attacks within 30 days prior to screening.
6. Have, as determined by the Investigator and/or the Sponsor's medical monitor, any surgical or medical condition that could interfere with the administration of study drug or interpretation of study results.

Additional Exclusion Criteria (Disqualifying from Randomization)

7. Have any active infectious illness or fever defined as an oral temperature $>38^{\circ}\text{C}$ (100.4°F), tympanic $>38.5^{\circ}\text{C}$ (101.3°F), axillary $>38^{\circ}\text{C}$ (100.4°F), or rectal/core $>38.5^{\circ}\text{C}$ (101.3°F) within 24 hours prior to the first dose of study drug in Treatment Period 1.
8. Have had signs or symptoms of an angioedema attack within 2 days prior to the first dose of study drug in Treatment Period 1.

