Analysis of efficacy endpoints will employ descriptive statistics and will include all subjects randomized and treated with study drug. If warranted by the data, the comparison of CINRYZE doses will employ a paired t-test to perform a two-sided test of superiority (1000 U vs. 500 U) conducted at $\alpha=0.10$.

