2.5 Determination of Sample Size

This study is designed to assess the safety, tolerability, and relative efficacy of two different doses (500 U and 1000 U) of CINRYZE as prevention therapy for angioedema attacks in children 6 to 11 years of age with HAE. Twelve subjects will be randomized in this study. Given the limited number of pediatric subjects with HAE who will fall within this age category and have a history of angioedema attacks appropriate to meet study inclusion criteria (Caballero, 2012), this number is considered a reasonable target with respect to the ability to enroll eligible subjects.

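### The formal dose comparison is a paired t-test without a period term, and the SAP does not say whether it or the planned period-adjusted model decides

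*SAP*

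**What the plan says.** Protocol 7.3 and the synopsis plan descriptive statistics and one conditional test: "the comparison of CINRYZE doses will employ a paired t-test", two-sided, at alpha 0.10. They name no other dose test.

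SAP 10.1 repeats that test, stating that "the comparison of CINRYZE doses will employ a paired t-test to perform a two-sided test of superiority (1000 U vs. 500 U". It then adds a condition on completers: "conducted at $\alpha=0.1$, this comparison will be performed only if the final sample size has 12 or more complete subjects with both period data". The parameter tested "is the population mean of within subject treatment difference for the primary efficacy variable". It is estimated by summing each child's 1000 U value minus 500 U value and dividing by N, with a 90% CI. Neither sequence nor period enters the formula.

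SAP 10.1 then tests treatment at alpha 0.10 in a mixed model "with period, treatment and treatment sequence as fixed effects, and subject nested within sequence as random effect", with a 90% CI for the same dose difference. Both methods are to be repeated in the first sensitivity analysis, which leaves out attacks in the first 2 weeks of Period 2. A second leaves out the first 2 weeks of both periods. SAP 20.1 lists the mixed-model output as Tables 3.3, 3.3a and 3.3b.

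No sentence ranks the two methods. SAP section 17, on changes from the protocol, covers analysis populations only and does not mention the mixed model.

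**The concern.** In a two-period crossover, each child's dose difference also contains the difference between periods, with opposite sign in the two sequences. The plain mean cancels it only when the sequences are equal in size. Even then it stays in the SD of the differences, so the standard error is too large for the dose question.

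The formal hypothesis is tied to the version that ignores this. The version that handles it is planned at the same alpha without a stated role. If the two disagree, the dose conclusion depends on which is quoted.

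**Working it through.** **Inputs.** N = 12: SAP 2.5 states "Twelve subjects will be randomized in this study", on the ground that "this number is considered a reasonable target with respect to the ability to enroll eligible subjects". Alpha is 0.10 two-sided (SAP 10.1). Assignment is with equal probability from a schedule held at each site (Protocol 5.2, SAP 2.2); no block size or overall balancing is stated. The documents give neither the SD of the within-child difference (σ) nor the period effect P (Period 2 minus Period 1). I work in units of σ and assume P from 0 to 1.

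**The plan's own figure.** There is no power calculation to reproduce. The stated alpha does reproduce: with P = 0 the paired t-test on 11 df rejects at 0.100.

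**Model.** Let d be the 1000 U value minus the 500 U value, τ the dose effect and σ the SD of d within a sequence. Then d has mean τ + P in sequence A/B (1000 U in Period 2) and τ − P in B/A.

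- Paired mean: E(d̄) = τ + P(nAB − nBA)/N.
- Variance used by the paired test: E(s²) = σ² + 4·nAB·nBA·P²/[N(N − 1)]. At 6:6 this is 1 + 144P²/132, so 1.27 at P = 0.5 and 2.09 at P = 1.0.
- Period-adjusted estimate: half the sum of the two sequence means of d, which has mean τ for any P. Its SE is (σ/2)√(1/nAB + 1/nBA), on 10 df. With complete data this is normally what the SAP's mixed model gives.

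**Size of the paired test at nominal 0.10**, by numerical integration, agreeing with 200,000 simulated trials per setting:

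| Split | Absolute bias of paired mean | Size, P = 0.5 | Size, P = 1.0 | Chance of split |
|---|---|---|---|---|
| 6:6 | 0 | 0.067 | 0.021 | 924/4096 = 0.226 |
| 7:5 | P/6 | 0.077 | 0.040 | 1584/4096 = 0.387 |
| 8:4 | P/3 | 0.110 | 0.116 | 990/4096 = 0.242 |
| 9:3 | P/2 | 0.168 | 0.279 | 9:3 or worse: 598/4096 = 0.146 |

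The last column assumes 12 independent 1:1 draws. The documents do not exclude blocking within site, which would change these probabilities. The period-adjusted test had simulated size 0.099 to 0.102 at every split and every P tried.

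**Power at 6:6 for τ = 0.6σ.** Paired: 0.54 at P = 0.5 and 0.33 at P = 1.0. Adjusted: 0.61 in both cases.

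**Cost of adjusting when P = 0, τ = 0.6σ.** Paired power is 0.619 at every split. Adjusted power is:
- 6:6: 0.614, a loss of 0.5 point
- 7:5: 0.604, a loss of 1.5 points
- 8:4: 0.572, a loss of about 5 points
- 9:3: 0.513, a loss of about 11 points

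**Two tests, no rule.** With no period effect and no dose effect, at least one of the two tests rejects in 0.108 of simulated trials at 6:6 and 0.128 at 8:4.

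**The case against.** Much of the protection is already planned. The period-adjusted model is in SAP 10.1 for the main analysis and extends to the sensitivity analyses, and SAP 18.1 displays results by sequence and period. A reader might infer that the plan ignores period effects; it does not. What it lacks is a statement of which analysis decides.

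The paired test is also hedged. The analysis is mainly descriptive, and the test runs only if the data justify it and 12 children complete both periods. Twelve are to be randomized and the current protocol has no replacement provision, so one dropout would remove the test. The SAP itself says that power is low.

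A reader might infer that the paired test generally gives too many false positives. The figures do not support that: inflation is clear only from 9:3, and averaged over independent 1:1 assignment the size is 0.100. The bias at the realised split stands, because the trial is reported at one split.

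A reader might also infer that the design makes a period effect likely. The documents do not establish that:
- Selection on a high baseline attack rate lowers later rates, but if rates are otherwise stable it affects both treatment periods alike.
- Starting Period 2 on the other dose is carryover, which a period term does not remove.
- Starting Period 1 off study drug is transient. With a half-life of about 60 hours (Protocol 1.1.2), five half-lives are 300 hours or 12.5 days, inside the 2 weeks that the second sensitivity analysis leaves out.
- The recent-attack exclusion in Protocol 4.2 ("Have had signs or symptoms of an angioedema attack within 2 days prior to the first dose of study drug in Treatment Period 1") applies to Period 1 only, but pushes its attack rate the opposite way from starting off drug.

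Finally, P = 1.0 may be large. For scale, Protocol Table 4 gives a mean of 0.35 and SD of 0.453 attacks per month at ages 6 to 11 in an earlier study. With an assumed within-child correlation r from 0 to 0.8, σ = 0.453√(2(1 − r)) runs from 0.64 down to 0.29, so P = 1.0 is about 80% to 180% of that mean. Three of those nine children had no attacks, so the normal model is rough.

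**Conclusion.** The point holds as a gap in specification. The hypothesis, estimate and 90% CI sit on a contrast that is biased by P(nAB − nBA)/12 at unequal splits and conservative at 6:6 whenever P is not zero. A period-adjusted test of the same difference stands beside it with no stated role.

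The bias formula needs only an additive period effect. The sizes and powers rest on an assumed P of 0 to 1 SD and normal differences; the split probabilities rest on simple 1:1 assignment. Within those assumptions, the likelier harm near balance is lost power. An inflated error rate needs a split of about 9:3 or worse.

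**What to change.** In SAP 10.1, name the dose contrast from the mixed model with period as the single alpha 0.10 test and the source of the dose estimate and 90% CI, for the main analysis and both sensitivity analyses. Keep the paired t-test as a supportive, unadjusted display. Restate the hypothesis for the period-adjusted contrast, and say whether the 12-completer condition applies to it, since that condition is written only for the paired comparison.

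Change Protocol 7.3 and the synopsis at the next amendment, or list the change in SAP section 17.

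The cost is wording, since the model and its tables are already planned, plus the power loss shown above if there is no period effect. The change does not deal with carryover, which still depends on the sensitivity analyses.

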While CINRYZE has proven to be safe and effective in adults and adolescents, questions remain about the ideal pediatric dosing regimens, particularly for young and/or light-weight children. Additional information with regards to the pharmacokinetics and dosing of CINRYZE in children (≥ 2 to < 12 years of age) is currently being assessed in a study for the treatment of acute angioedema attacks (Protocol 0624-203). Dosing in study 0624-203 is determined by subject weight category; 10 kg to 25 kg inclusive (500 U and 1000 U) and > 25 kg (1000 U and 1500 U).

The aim of this study is to assess the safety and tolerability, relative efficacy, and PK/PD of two different doses (500 U and 1000 U) of CINRYZE administered by IV injection to further the knowledge of the management of HAE in children 6 to 11 years of age. Consistent with the recent consensus on therapeutic strategies for children and adolescents with HAE ([Wahn et al., 2012](#)), the current study will account for differences in body weight by administering 2 fixed doses of CINRYZE (500 U and 1000 U), and CINRYZE dosage will be related to plasma volume, body surface area, and body mass index. The optimal dose for this age group

may be less than the IV dose of 1000 U every 3-4 days approved for adult and adolescent patients and the proposed study allows a within subject comparison of the effectiveness and tolerability of two dosing regimens. In addition, the study will provide supportive data on potential immunogenicity and quality of life health status in this pediatric population, as well as prospective observational data on angioedema attack frequency in the “ultra-orphan” 6 to 11 years of age subgroup.

Detailed considerations regarding CINRYZE doses selected for this study are presented in Section 5.1.

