2.2 Randomization

Twelve subjects will be randomized to one of two treatment sequences, with each sequence consisting of two 12-week treatment periods. Randomization will occur on Dosing Day 1 (Visit 1a) of Treatment Period 1. Each investigative site will receive a randomization schedule which will be used to assign subjects at that site to one of two sequences (A/B or B/A), with equal probability. Treatment A will be 500 U CINRYZE administered intravenously twice weekly (every 3 or 4 days) for 12 weeks and Treatment B will be 1000 U CINRYZE administered intravenously twice weekly (every 3 or 4 days) for 12 weeks.

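### The exploratory U/kg slope in SAP 10.1 blends the randomised within-child dose contrast with non-randomised differences between lighter and heavier children

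*SAP*

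**What the plan says.** SAP 10.1 introduces these analyses as exploratory: "The following analyses will be performed to explore the potential weight-adjusted dose response relationship in efficacy". The exposure is the period's dose, 500 U or 1000 U, divided by the weight taken before the first dose of that period.

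Two models are planned:
- a slope on continuous U/kg, fitted "with period, dose and treatment sequence as the fixed effects and subject nested within sequence as random effect";
- six pairwise differences between U/kg quartile groups, fitted "with period, dose group and treatment sequence as the fixed effects, and subject nested within sequence as random effect".

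The word dose in the slope model is read here as the continuous weight-adjusted dose, which is the natural sense of the sentence. Neither model contains weight, age, the child's mean U/kg or fixed subject effects, and no other SAP section adds them.

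Under SAP 2.2, what is randomised is the order of two fixed doses, to "one of two sequences (A/B or B/A), with equal probability". Weight is neither randomised nor a stratum. Protocol 1.2 gives the background: "questions remain about the ideal pediatric dosing regimens, particularly for young and/or light-weight children".

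**The concern.** U/kg has a randomised numerator and a non-randomised denominator. Within a child, moving from 500 U to 1000 U changes U/kg by random assignment. Between children, U/kg differs because some are lighter, and usually younger, than others. A random subject intercept uses both sources and returns one slope.

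If heavier children have more attacks for reasons unrelated to dose, the model credits part of that pattern to low U/kg and suggests a benefit of higher U/kg. If heavier children have fewer attacks, it hides part of a real benefit. The issue matters because the analysis bears on dosing by weight, where the protocol says questions remain.

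**Working it through.** The plan states no precision or power for this slope, and N is justified by feasibility, so there is no figure to reproduce.

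**Inputs from the documents**
- Model terms: SAP 10.1. Randomisation of order only: SAP 2.2.
- 12 children, hence 24 child-periods: SAP 2.5.
- SD 0.453 attacks/month (mean 0.35), ages 6-11: Protocol Table 4. Used only to scale the simulation.

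**Assumptions, not in the documents**
- Weights uniform over 20-35, 20-45 or 20-60 kg, constant across the two periods.
- ICC 0.2, 0.5 or 0.8.
- Trend g = 0.2 attacks/month per 10 kg (0.02 per kg), and no dose effect.

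**1. Split the exposure.** A child of weight W has U/kg values 500/W and 1000/W: a randomised difference of 500/W and a non-randomised mean of 750/W. At 25 kg the values are 20 and 40 (mean 30). At 50 kg they are 10 and 20 (mean 15). The 25 kg child on 500 U and the 50 kg child on 1000 U are treated as equally exposed.

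**2. What the model estimates.** With total variance 1, a child's period difference has variance 2(1-ICC) and the child's mean has variance ICC + (1-ICC)/2. Let I_w be the sum of squares of ±500/W after removing period, divided by the first variance. Let I_b be the sum of squares of 750/W after removing sequence, divided by the second. Then

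slope = (1-s) × within-child slope + s × between-child slope, with s = I_b/(I_w + I_b).

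**3. False slope with no dose effect.** The within-child slope is then zero on average. Because 750/W falls by 750/W² per kg, the between-child slope is about -g·W²/750. At W = 30 this is -0.02 × 900/750 = -0.024 per U/kg, or -0.24 per 10 U/kg. Averages over 2,000 random sets of 12 weights, in attacks/month per 10 U/kg:

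| Weights (kg) | Between-child slope | s at ICC 0.2 / 0.5 / 0.8 | False slope at ICC 0.2 / 0.5 / 0.8 |
|---|---|---|---|
| 20-35 | -0.19 | 11% / 6% / 2% | -0.021 / -0.011 / -0.004 |
| 20-45 | -0.25 | 20% / 12% / 4% | -0.050 / -0.029 / -0.010 |
| 20-60 | -0.35 | 31% / 19% / 7% | -0.106 / -0.063 / -0.024 |

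The last column averages the product set by set, so it can differ slightly from the product of the averages. Weights spaced evenly over each range raise s to 14/8/3%, 26/15/5% and 39/24/9%, and the largest false slope to about -0.12. With g = 0 the false slope is zero in every cell.

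**4. Simulation with estimated variances.** REML, 1,000 trials per setting, SD 0.453, two-sided alpha 0.10, same trend:
- 20-45 kg: bias -0.044, -0.024, -0.010; rejection 0.16, 0.11, 0.11 (ICC 0.2, 0.5, 0.8).
- 20-60 kg: bias -0.082, -0.054, -0.021; rejection 0.21, 0.18, 0.14.
- No trend: no bias; rejection 0.09 to 0.12.

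These biases are no larger than those in step 3, because the trend also inflates the estimated between-child variance and so shifts the slope toward the within-child part. With a true slope of -0.1 (20-45 kg, ICC 0.5), the planned model averages -0.123 under a trend of +0.2 and -0.075 under -0.2.

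**5. After separating the parts.** The within-child slope uses I_w alone, so its standard error rises by 1/√(1-s): 1/√0.69 = 1.20 at s = 31%, and 1/√0.98 = 1.01 at s = 2%. In the simulations with no dose effect, adding the child's mean U/kg, or weight, leaves a bias of at most 0.007 and rejection of 0.09 to 0.11. For a true slope of -0.1 with no trend (20-45 kg, ICC 0.5), power is 0.38 as planned, 0.36 with the child's mean U/kg and 0.35 with weight.

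**6. Quartile groups.** At 20-35 kg, 500 U spans 500/35 = 14.3 to 500/20 = 25 U/kg, and 1000 U spans 28.6 to 50. There is no overlap: groups 1 and 2 are the heavier and lighter halves on 500 U, and groups 3 and 4 the same halves on 1000 U. Contrasts 1 vs 3 and 2 vs 4 are within-child; 1 vs 2 and 3 vs 4 compare heavier with lighter children on one dose. At 20-60 kg about 85% of 500 U observations still fall in the lower two groups. Adding weight at 20-35 kg raises the standard errors of 1 vs 2, 3 vs 4, 1 vs 4 and 2 vs 3 by about 60-80%. At 18-45 kg the rise is about 4-21%.

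**The case against.** The strongest reply is that mixing is not bias. Bias needs a relation between attack rate and weight apart from dose, and the documents report none. This stands, and it is why the size can only be given as a range.

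A reader might infer such a trend from Protocol Table 4, where the mean monthly rate on CINRYZE is 0.35 at ages 6-11 and 0.71 at ages 12-17. The table does not support that inference. Most infusions in the programme were 1000 U, so the older group also tended to receive fewer U/kg, and the comparison says nothing about a trend within ages 6-11.

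Second, if U/kg truly drives response, differences between children are signal, and the within-child slope is essentially the 1000 U versus 500 U contrast rescaled by weight. This is a fair point about the estimand. It argues for showing both slopes, not for pooling them unseen.

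Third, the analysis is exploratory, with no decision rule attached, and it is not the only evidence on weight. The SAP also plans a scatter plot of attacks against U/kg, individual listings, change from the observation period, and population pharmacokinetic modelling. This stands and limits the importance. None of these items separates the two components of the fitted slope.

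Fourth, a weight term in the quartile model would remove much of the information in four of its six contrasts. This stands.

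**Conclusion.** The point holds for the continuous U/kg slope, as a minor improvement to an exploratory analysis. That the planned model pools randomised and non-randomised information follows from its terms. Whether the pooled slope is biased depends on a weight or age trend that the documents neither give nor exclude. Under the assumed trend of 0.2 attacks/month per 10 kg, the false slope runs from about -0.004 (20-35 kg, ICC 0.8) to about -0.11 (20-60 kg, ICC 0.2) attacks/month per 10 U/kg. A narrow weight range or a high ICC makes the problem small.

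Two stronger readings should be avoided. A reader might infer that the trial's main dose comparison is confounded by weight. It is not: the paired 1000 U versus 500 U difference compares each child with himself or herself. A reader might also infer that the planned slope is certainly wrong or its test grossly inflated. With no trend it is unbiased, and at 20-45 kg with ICC 0.5 or more its rejection rate under the assumed trend is about 0.11 against a nominal 0.10.

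**What to change.** In the slope model of SAP 10.1, replace U/kg by two terms: the child's mean U/kg over the two periods, and the period's deviation from that mean. Name the within-child slope as the dose-response estimate and show the between-child slope beside it, marked as non-randomised. Adding period-specific baseline weight is a close alternative but not an identical one, because a linear weight term does not reproduce 750/W exactly.

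No new data are needed: weight is scheduled at Visits 1a and 1b in Protocol Schedules 2 and 3. The cost is one degree of freedom and a slope standard error about 1% to 20% larger under the ranges above.

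Do not add weight to the quartile-group model. Label its six pairwise differences as descriptive, and state that 1 vs 2 and 3 vs 4 are largely contrasts between heavier and lighter children.
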